#### 4.8 Efficacy Analyses

##### 4.8.1 Primary Efficacy Analysis

Primary efficacy analysis will be the comparison of change in ISQ highest value for coated implant with change in ISQ highest value for the uncoated implant on the “index implant” from day 1 to 12 weeks visit with Fisher’s non-parametric permutation test on the ITT-population at significance level 0.05. For primary efficacy variable the 95% confidence interval for the mean difference between the coated and the uncoated implants is obtained by inversion of Fisher’s non-parametric permutation test by means of simulation.

If the 12 weeks ISQ highest values are missing Last observation carry forward (LOCF) will be used from 8 weeks, if available. For the cases of implant loss ISQ = 0 at 12 weeks will be imputed in the main analysis, i.e. resulting in negative difference in ISQ for the subject. For the cases where week 8 and week 12 values are not available due to other reasons than implant loss, same value as baseline value will be imputed, i.e. the difference of 0 will be imputed.

Primary efficacy analysis will be presented per centre and a separate analysis will also be performed in order to study centre effect for primary variable. In case of few centres, centre will be analyzed as fixed effect.

If significant differences are found between the two randomised groups in important baseline predictors a complementary primary efficacy analyses will be performed adjusted for these variables using analysis of covariance (ANCOVA).

Following sensitivity analyses will be performed for the primary efficacy variable:

- Multiple imputations: using analysis of variance for the unadjusted analysis and analyses of covariance for the adjusted analysis if needed. When using multiple imputations LOCF should not be applied. For the sensitivity analysis missing values due to lost implants will be handled with multiple imputation. Following rules will be applied:
  - The multiple imputation will be performed separately for the two study treatment groups to avoid cross-contamination of imputation models between the groups, using PROC MI procedure in SAS version 9.4 and fully conditional specification (FCS) with regression method (REG), per treatment group.
  - The following seed will be used for both groups: 545399
  - The outcome variable of change in ISQ from day 1 will be imputed

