  - All baseline characteristics, baseline ISQ value and any follow-up ISQ will be included if they are associated with at least  $r \geq 0.40$  to the difference in ISQ at 12 weeks or the actual ISQ value at 12 weeks, or if the variables are

STATISTISKA KONSULTGRUPPEN		Statistical Analysis Plan	
Protocol: A randomized, double blind, parallel study to evaluate the performance and safety of the Zolidd One ExHex dental implant in subjects with partial edentulism		Protocol No: ADD-001	Version: 1.0 Page 13 of 18

associated with the missingness of the difference in ISQ at of at least 0.10 significance level.

- 50 study samples will be imputed and pooled by using PROC MIANALYZE procedure
- Trace plots of means and standard deviations of imputed variables will be reviewed checking that the multiple imputation has worked properly
- Worst case scenario analysis: using the same imputation rules as specified above for the coated implant group, but imputing the difference in ISQ equal to 0, i.e. impute baseline value for week 12 visit, for uncoated implant group no matter the reason for missing data (also for implant loss).

Complementary analyses between the two randomized groups of the primary efficacy variable will be done on the PP-population.

The results from the analyses of primary variable will be given both in tables and figures.

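### One seed for two separate imputation runs can make the imputation noise cancel between arms, leaving the pooled SE of the multiple-imputation sensitivity analysis slightly too small

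*SAP*

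**What the plan says.** The rules are in SAP 4.8.1, under the sensitivity analyses of the primary variable.

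- Separation of the arms: "The multiple imputation will be performed separately for the two study treatment groups to avoid cross-contamination of imputation models between the groups". The method is fully conditional specification with regression in PROC MI.
- Seed: "The following seed will be used for both groups: 545399".
- Target: "The outcome variable of change in ISQ from day 1 will be imputed".
- Pooling: "50 study samples will be imputed and pooled by using PROC MIANALYZE procedure".
- Analysis model: "Multiple imputations: using analysis of variance for the unadjusted analysis and analyses of covariance for the adjusted analysis if needed".
- What counts as missing: "When using multiple imputations LOCF should not be applied", and "For the sensitivity analysis missing values due to lost implants will be handled with multiple imputation". Subjects who would be filled in by a fixed rule in the main analysis are therefore multiply imputed here.

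Baseline characteristics, baseline ISQ and follow-up ISQ enter the imputation model only if they pass a correlation threshold or are associated with missingness. The SAP does not say whether that selection is made per arm, whether the two arms are two procedure calls or one call with by-group processing, or whether the random stream carries on from the first arm to the second. No second seed is given.

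**The concern.** Pooling by Rubin's rules adds the between-imputation variance B to the within-imputation variance W. For a difference of two arm means, B should be the sum of the imputation noise from each arm, which requires the draws in the two arms to be independent.

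Two runs started at the same seed use the same sequence of random numbers. If both runs consume that sequence in the same pattern, the k-th imputed data set carries nearly the same random disturbance in the coated and uncoated arms. The disturbances subtract out of the treatment difference, B collapses towards zero, and the pooled SE loses the component that multiple imputation is meant to supply. Separate imputation was chosen to keep the arms apart; a shared seed can link them again through the random draws.

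At stake are the confidence interval and p-value of one sensitivity analysis. The planned trace plots would not reveal the fault, because they check the imputed variables and not the correlation between the two arms' draws.

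**Working it through.** **Inputs from the documents.** 31 randomised per arm, SD of change 5.6, 28 evaluable per arm for 90% power at a difference of 5, and 10% dropout (SAP 1.4); dropout expected below 5% (protocol 18.10); 50 imputations (SAP 4.8.1).

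**Assumptions.** The number missing per arm, k, is not known and is shown over a range. In the simulations, the baseline ISQ distribution and its correlation with change (about 0.5 in size) are assumed.

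**Plan's own figure.** Two-sided 0.05, difference 5, SD 5.6: noncentral-t power is 0.896 with 27 per arm and 0.907 with 28. The stated 28 is reproduced.

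**Formula check, no predictor.** With n = 31 and m = 50:

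- W = 2 × 5.6² / 31 = 2.023.
- Imputation noise per arm = (k/n)² × 5.6² × (1/(n−k) + 1/k).
- Independent streams: B is twice that. Identical streams: B is about 0.
- T = W + (1 + 1/50) × B, and SE = √T.

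For k = 3, noise per arm = (3/31)² × 31.36 × (1/28 + 1/3) = 0.1084. So B = 0.217, T = 2.023 + 1.02 × 0.217 = 2.244 and SE = 1.498. With identical streams, SE = √2.023 = 1.422. The shortfall is 1 − 1.422/1.498 = 5.1%.

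| Missing per arm | B, independent | SE, independent | SE, identical | Shortfall |
|---|---|---|---|---|
| 1 | 0.067 | 1.446 | 1.422 | 1.7% |
| 2 | 0.140 | 1.472 | 1.422 | 3.3% |
| 3 | 0.217 | 1.498 | 1.422 | 5.1% |
| 6 | 0.486 | 1.587 | 1.422 | 10.4% |

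**Simulation, one baseline predictor, no true effect.** This used Bayesian regression imputation per arm, with either a restarted seed or one continuing stream. The generator was numpy's, not that of SAS.

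| Missing | Stream | Correlation of arms' imputed means | B | Mean SE | Empirical SD | Type I error |
|---|---|---|---|---|---|---|
| 3 and 3 | same seed | 0.96 | 0.010 | 1.429 | 1.478 | 5.7% |
| 3 and 3 | continuing | 0.00 | 0.174 | 1.486 | 1.479 | 4.7% |
| 6 and 6 | same seed | 0.96 | 0.026 | 1.443 | 1.551 | 6.4% |
| 6 and 6 | continuing | 0.00 | 0.395 | 1.567 | 1.553 | 4.7% |

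These rows rest on 8,000 replicates. The shortfall is 1 − 1.429/1.486 = 3.8% at 3 per arm and 1 − 1.443/1.567 = 7.9% at 6. At 2 per arm (2,500 replicates) it is 1 − 1.425/1.462 = 2.5%. A predictor lowers the shortfall because it lowers the imputation noise.

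**What breaks the synchrony.**

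- Unequal counts (2 v 4, or 3 v 4): correlation 0.01 to 0.05, almost no effect on the SE.
- Equal counts but a predictor in one arm only: correlation 0.04, almost no effect.
- Week-8 ISQ as an imputed predictor (40 replicates, assumed correlations, 3 missing at week 12 per arm): with week-8 counts of 0 v 1 the shortfall is 0.03%, with 2 v 1 it is 0.4%, and with matching counts it stays at 2.5 to 3.6%.
- Unequal arm sizes alone (30 and 32, 3 missing each) do not break it: correlation 0.96 to 1.00.

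**How often counts match.** Taking missingness as binomial in 31 per arm, P(equal and non-zero) = Σ p(k)² over k ≥ 1. This gives 17%, 20%, 17% and 14% at 3%, 5%, 10% and 15% missing. Exactly 3 and 3 has probability 5.5% at 10% missing and 1.8% at 5%. Exactly 6 and 6 has 0.3% and 0.001%. At 5% missing, 1 and 1 makes up 11.1/20.0 = 55% of the matching cases. If 30 to 50% of subjects missing week 12 also lack week 8 (an assumption), the chance that both counts match falls to about 6% at 10% missing and 9 to 10% at 5%.

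**The case against.** The strongest reply is that the text does not prove the fault. Imputing per treatment group under one seed also describes a single procedure call with arm as by-variable. If the stream carries on from one arm to the next in such a run, the draws are independent. How the software treats the stream across by-groups is stated nowhere in these documents, and the simulations did not use its generator. This stands as a limit. Even so, "The multiple imputation will be performed separately for the two study treatment groups" together with one seed for both groups reads more naturally as two runs from the same start, and the formula results do not depend on any generator.

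The second reply is that the trigger is narrow. Equal week-12 counts are not enough: predictors are selected from the data, and an incomplete week-8 ISQ consumes draws of its own. This also stands, so 14 to 20% is a ceiling and not an estimate.

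The third is that nothing decisive depends on this analysis. That is right. The primary test is a permutation test with fixed imputed values, and the multiple-imputation analysis is one of two sensitivity analyses that the SAP lists without ranking. The worst-case analysis has no random draws if the rules it refers to are the fixed ones of the main analysis.

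A reader might infer that the shared seed makes this analysis generally anti-conservative, or that its p-value is badly wrong. The documents do not support that. With unequal counts or different models the effect vanishes, and at 3 missing per arm type I error was 5.7% against 4.7% in the largest run and 4.5% against 3.5% in a smaller one. That is too small a change to rest the point on.

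**Conclusion.** The point holds as a minor, conditional defect of specification. If the arms are run as two calls from seed 545399, and if week-12 missing counts, model structure and missing counts in imputed predictors all match, nearly all of B is lost. The pooled SE is then about 1.5 to 5% too small at 1 to 3 missing per arm, the range implied by the plan's dropout figures of under 5% and 10%. The 8 to 10% shortfall at 6 per arm is a bound for an unlikely case. The loss of B and the SE shortfall are the firm results; inflation of type I error at planned dropout is barely measurable.

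The conclusion rests on the two-call reading, on assumed missing counts, and on simulations with assumed correlations. It does not touch the primary permutation test or the sample size. It is worth correcting because the fault would give no warning, and because an analyst who noticed it later could change the seed only by departing from the SAP.

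**What to change.** In SAP 4.8.1, give a different seed for each treatment group. Alternatively, state that both arms are imputed in one seeded run with arm as by-variable, and confirm in the program that the random stream continues from one arm to the next and does not restart. Two seeds are simpler because they need no such confirmation.

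The cost is one number or one sentence, made before unblinding. Data, power and trial conduct are not affected.

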#### 4.8.2 Secondary Efficacy Analyses Part I

Secondary efficacy analyses for Part I will be the comparison between the two randomized groups regarding all the secondary efficacy variables given in section 3.2.2 using the statistical methodology given in sections 4.1 above on the ITT-population.

Complementary analyses between the two randomized groups of secondary efficacy variables will be done on the PP-population.

#### 4.8.3 Secondary Efficacy Analyses Part II

Secondary efficacy analyses for Part II will be the comparison between the two randomized groups regarding all the secondary efficacy variables given in section 3.2.3 using the statistical methodology given in sections 4.1 above on the ITT-population.

Complementary analyses between the two randomized groups of secondary efficacy variables will be done on the PP-population.

#### 4.8.4 Exploratory Efficacy Analyses

Univariable and multivariable analyses of baseline predictors to primary efficacy variable will be performed using mixed models as specified in *General Methodology* above followed by forward stepwise multivariable model on the ITT population on all implants. The variables to be examined are:

- Age
- Sex
- Bone quality
- Bone quantity
- Implant position
- Smoking
- Alcohol
- Diabetes.

STATISTISKA KONSULTGRUPPEN		Statistical Analysis Plan	
Protocol: A randomized, double blind, parallel study to evaluate the performance and safety of the Zolidd One ExHex dental implant in subjects with partial edentulism		Protocol No: ADD-001	Version: 1.0 Page 14 of 18

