18.5.4 Exploratory performance analyses

Univariable and multivariable analyses of baseline predictors to primary and selected secondary outcome variables will be performed using linear and/or logistic univariable regression analyses followed by forward stepwise multivariable linear and/or logistic regression analyses.

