### 3.2.1 *Primary Efficacy Variable*

The primary endpoint is change in stability from day 1 to 12 weeks after implantation of the “index implant” comparing coated and uncoated implants. This will be assessed in terms of induced micro motion of the implant using the Osstell device. The ISQ values are recorded from two directions. The directions should be bucco-lingual and mesio-distal, whereof highest value of the two measurements will be used in the analyses.

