## 4 STATISTICAL METHODOLOGY

### 4.1 General Methodology

The design of the study is a two parallel group design. All main efficacy analyses will be performed on the ITT population. Complementary efficacy analyses will be performed on the PP population.

For comparison between the two groups (coated vs uncoated), when we have only one observation per subject, Fisher's non-parametric permutation test will be used for continuous variables, Fisher's exact test for dichotomous variables, Mantel-Haenszel chi-square test for ordered categorical variables and Chi-square test for unordered categorical variables.

For primary efficacy variables and for other important continuous efficacy variables the mean difference between the two groups with 95% confidence interval (CI) will be given. For dichotomous variables the percentage in each group together with the difference in percentage between the two groups with 95% confidence interval will be calculated with Miettinen and Nurminen's method.

If clinically relevant significant differences are found between the two randomised groups in important baseline predictors a complementary primary efficacy analyses will be performed

STATISTISKA KONSULTGRUPPEN		Statistical Analysis Plan	
Protocol: A randomized, double blind, parallel study to evaluate the performance and safety of the Zolidd One ExHex dental implant in subjects with partial edentulism		Protocol No: ADD-001	Version: 1.0 Page 11 of 18

adjusted for these variables using analysis of covariance (ANCOVA) for continuous outcome variables and with multivariable logistic regression for dichotomous outcome variables.

For comparison between the two groups (coated vs uncoated), when we have more than one observation for all or for some subjects, a mixed model with random effects will be used for continuous outcome variables and a General Estimating Equation (GEE) model is used for dichotomous outcome variables. In both these models the dependence within observation are taken into account correctly. For non-normal continuous variables the mixed model will include an empirical bias correction with robust standard errors.

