#### 4.8.5 Subgroup Analyses

Interaction analyses will be performed between baseline variables and group effect, coated vs uncoated, regarding primary efficacy variable on the ITT population.

Interactions effect with ( $p < 0.10$ ) will be followed by suitable subgroups analyses for that baseline variable.

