### 7 LISTING OF TABLE, FIGURES AND LISTINGS

#### 7.1 Listing of Tables

Table Number	Table Title
14.1.1	Patient Disposition and Data Sets Analysed (ITT Population)
14.1.2	Protocol Deviations Leading to Exclusion from PP Population (ITT Population)
14.1.3.1	Demographics and Baseline Characteristics (ITT Population)
14.1.3.2	Demographics and Baseline Characteristics (PP Population)
14.1.4	Medical History (ITT Population)
14.1.5	Surgical Data (ITT Population)
14.1.6.1	Prior Medications (ITT population)
14.1.6.2	Concomitant Medications (ITT population)
14.1.6.3	Dental Procedures (ITT population)
14.2.1.1	Primary Efficacy Analysis – Main and Sensitivity Analyses (ITT Population)
14.2.1.2	Primary Efficacy Analysis (PP Population)

STATISTISKA KONSULTGRUPPEN		Statistical Analysis Plan	
Protocol: A randomized, double blind, parallel study to evaluate the performance and safety of the Zolidd One ExHex dental implant in subjects with partial edentulism	Protocol No: ADD-001	Version: 1.0	Page 16 of 18

14.2.1.3	Secondary Efficacy Analysis (ITT Population)
14.2.1.4	Secondary Efficacy Analysis (PP Population)
14.2.2.1	Exploratory Analyses: Prediction of Max ISQ at 12 Weeks for VII Implants (ITT Population)
14.2.2.2	Exploratory Analyses: Prediction of Max Marginal Bone Height at 24 Months for All Implants(ITT Population)
14.2.3.2	Interaction Analysis and Subgroup Analysis (ITT Population)
14.3.2.1	Summary of Adverse Events (Safety Population)
14.3.2.2	Adverse Events, by System Organ Class and Preferred Term (Safety Population)
14.3.2.3	Adverse Events, by System Organ Class, Preferred Term and Maximum Reported Intensity (Safety Population)
14.3.2.4	Adverse Events, by System Organ Class, Preferred Term and Causality Assessment (Safety Population)
14.3.2.5	Serious Adverse Events, by System Organ Class and Preferred Term (Safety Population)
14.3.3	Adverse Events Leading to Discontinuation, by System Organ Class and Preferred Term (Safety Population)
14.3.4	Descriptive Statistics for Implant Status and Soft Tissue Status (Safety Population)
14.3.5	Descriptive Statistics for Dental Examinations (Safety Population)

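### SAP 4.8.4 models predictors of change in ISQ while Table 14.2.2.1 reports prediction of week-12 ISQ, and the listed model terms leave out treatment group

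*SAP*

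**What the plan says.** SAP 4.8.4 (Exploratory Efficacy Analyses) plans that "Univariable and multivariable analyses of baseline predictors to primary efficacy variable will be performed using mixed models", with the mixed models taken from General Methodology, "followed by forward stepwise multivariable model on the ITT population on all implants. The variables to be examined are" eight items: age, sex, bone quality, bone quantity, position of the implant, smoking, alcohol and diabetes. Neither treatment group nor day-1 ISQ is among them.

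The outcome named there is defined in SAP 3.2.1: "The primary endpoint is change in stability from day 1 to 12 weeks after implantation of the “index implant” comparing coated and uncoated implants". SAP 7.1 lists the ISQ output for the exploratory analysis as Table 14.2.2.1, "Exploratory Analyses: Prediction of Max ISQ at 12 Weeks for VII Implants (ITT Population". That is an absolute value, which SAP 3.2.2 treats as a separate, secondary variable for the index implant. A companion table, 14.2.2.2, covers marginal bone height at 24 months, which the text of 4.8.4 does not mention.

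Three other places bear on the point:
- SAP 4.1 introduces the mixed model with the words "For comparison between the two groups (coated vs uncoated), when we have more than one observation for all or for some subjects".
- SAP 4.8.5 plans a separate analysis: "Interaction analyses will be performed between baseline variables and group effect, coated vs uncoated, regarding primary efficacy variable on the ITT population".
- Protocol 18.5.4 is wider than the SAP text: "Univariable and multivariable analyses of baseline predictors to primary and selected secondary outcome variables will be performed". SAP section 6, which lists the changes from the protocol, does not mention the exploratory outcome.

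**The concern.** There are two distinct problems.

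The programmer is given two outcomes for one analysis. Change and week-12 level answer different questions. Good bone may raise ISQ at placement and at week 12, but raise it more at placement. It would then appear favourable for the week-12 value and unfavourable for change. The protocol presents the device as useful where bone quality is not optimal, so the direction reported for bone quality is likely to be read with interest.

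The models also pool arms that the trial is powered to separate by 5 ISQ units. A univariable model normally holds one predictor, and forward selection can only pick from its candidates. On the natural reading, treatment is therefore absent, and any real treatment effect goes into the error term of every predictor's coefficient.

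**Working it through.** **1. The plan's own figure.** Inputs from SAP 1.4 and 4.1: difference 5, SD of change 5.6, power 90%, two-sided 0.05.
- Normal approximation: n = 2 × [5.6 × (1.960 + 1.282)/5]² = 26.4, so 27 per group.
- With the t distribution: 27.4, so 28 per group, with power 0.907 at 28.

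The stated 28 is reproduced, so 5 and 5.6 can be used below, with the 62 subjects to be randomised.

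**2. Cost of leaving treatment out (outcome: change).** With 1:1 allocation, an omitted effect d adds d²/4 to the residual variance: residual SD = √(5.6² + d²/4). For d = 5 this is √(31.36 + 6.25) = √37.61 = 6.13 instead of 5.60, a ratio of 1.095.

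| True difference d | Residual SD, treatment omitted | Increase in SE |
|---|---|---|
| 0 | 5.60 | 0% |
| 2.5 | 5.74 | 2.5% |
| 5 | 6.13 | 9.5% |
| 7.5 | 6.74 | 20% |

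For a yes/no predictor split evenly over 62 subjects, with one implant each, SE = 2 × SD/√62. That is 1.42 with treatment in the model and 1.56 without it, at d = 5.

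The same loss can be expressed in two other ways, and these must not be added to it:
- As a share of outcome variance: 6.25/37.61 = 17%.
- As chance imbalance of treatment across the predictor: SD 5/√61 = 0.64 ISQ. This matches √(1.558² − 1.422²) = 0.64.

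For rarer predictors the imbalance term grows (0.80 at 20% prevalence, 1.07 at 10%). The SE itself grows by the same factor, 0.5/√(p(1 − p)), so the 9.5% does not change.

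**3. Effect of the outcome mismatch.** Let a predictor shift day-1 ISQ by a and week-12 ISQ by b. Its coefficient is b for the week-12 value and b − a for change. The signs differ when 0 < b < a.

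The documents give neither a nor b, so the values below are assumptions that span the cases. They were simulated with 62 subjects, an evenly split predictor, a treatment effect of 5, and SD 5.6 at each visit with correlation 0.5, which gives an SD of change of 5.6 × √(2 × 0.5) = 5.6. Each row used 4,000 runs.

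| a | b | Mean coefficient, week-12 value | Mean coefficient, change |
|---|---|---|---|
| 0 | 3 | +3.0 | +3.0 |
| 2 | 4 | +4.0 | +2.0 |
| 3 | 3 | about +3 | about 0 |
| 6 | 3 | +3.0 | −3.0 |

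In the last row, without treatment in the model, the change coefficient was negative in 97% of runs and the week-12 coefficient in about 3%. Adding treatment left all the means where they were. It lowered the SD of the change coefficient from about 1.56 to about 1.44. So the added noise comes only from omitting treatment, and the reversal comes only from the choice of outcome.

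**4. Does adding day-1 ISQ settle it?** Let β be the slope of week-12 ISQ on day-1 ISQ. Adjusted for day-1 ISQ, the coefficient for the week-12 value is b − βa. For change it is (b − a) − (β − 1)a = b − βa, which is identical. With a = 6 and b = 3 it is 3 − 6β: positive for β below 0.5 and negative above. The two outcomes agree because both have been replaced by a third quantity.

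**The case against.** The strongest reply is that 4.8.4 never says treatment is excluded. It lists predictors to be examined, which need not be every term in the model, and it borrows a mixed model that SAP 4.1 introduces for comparing coated with uncoated. That stands to this extent: omission is an inference from the list and from the univariable step, not a statement in the SAP. It does not remove the point, because two programmers could read the section differently.

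Both outcomes also fall within the scope of Protocol 18.5.4, and the analysis is labelled exploratory. That is correct, and it limits the consequence. It does not tell the reader of Table 14.2.2.1 which outcome was modelled.

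Three stronger readings are tempting, and the documents do not support them:
- A reader might infer that omitting treatment biases the predictors or causes the sign change. Under randomisation it does neither in expectation.
- A reader might infer that this is the only planned analysis using bone quality. It is the only SAP analysis that names it. However, the covariate adjustment and the imputation screening in SAP 4.8.1, and the interactions in 4.8.5, refer to baseline predictors, characteristics or variables in general and could include it.
- A reader might infer that day-1 ISQ should be forced into every model. It is measured after placement and plausibly lies on the path from bone quality to later stability. Adjusting for it asks for the effect given primary stability, which neither the text nor the table states as the question.

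**Conclusion.** The point holds as two separate and modest defects in an exploratory analysis.

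The contradiction between the outcome in the text and the outcome in the table title is documented. It can reverse the reported direction of a predictor if 0 < b < a, a condition that the documents neither establish nor rule out.

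The missing treatment term is the natural reading, not an explicit rule. If treatment is left out, predictor SEs for change are about 9.5% larger at the design effect, with a range of 0% to 20% for true differences from 0 to 7.5. There is no bias in expectation. These figures assume one implant per subject. The analysis is on all implants, where the omitted effect would go into the between-subject variance, and the documents give no within-subject correlation with which to size that.

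The primary test and the secondary group comparisons are unaffected. A reader might take the 17% variance share or the 0.64 ISQ imbalance as further harm, but both restate the 9.5%.

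**What to change.** Two edits to the SAP:

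- In 4.8.4, state that randomised treatment group is a forced fixed term in every univariable and stepwise model and is not subject to selection.
- Name one outcome in both places. The simplest way is to retitle Table 14.2.2.1 as prediction of change in max ISQ from day 1 to week 12, calculated per implant because the analysis covers all implants. Alternatively, state in 4.8.4 that both change and the week-12 value are reported, each in its own labelled table.

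A model that also adjusts for day-1 ISQ may be shown as an additional analysis, labelled as the effect given primary stability, and not as a replacement.

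The cost is a few lines of SAP text, one table title and one extra model term. No new data are needed.
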